Document ref: CIP summary from BVE-01- v2.0

Date: 14Feb2022

CIP SUMMARY

| Clinical Investigation code | BVE-01 |
|---|--|
| Title | Clinical Evaluation of the BlueDop Vascular Expert for Assessing Peripheral Arterial Disease |
| Objectives | Primary objective: Evaluate the clinical equivalence (assessment of accuracy) of BVE as binary result (either presence or absence of significant peripheral arterial disease) compared to arterial duplex ultrasound in a group of patients referred for evaluation of PAD of the lower limbs when performed by a vascular specialist. |
| | Secondary objectives: Evaluate the clinical equivalence (assessment of accuracy) of BVE as binary result (either presence or absence of significant peripheral arterial disease) compared to ABPI in a group of patients referred for evaluation of PAD of the lower limbs when performed by a vascular specialist. Assess the safety of the BVE device. |
| | Exploratory objectives: Evaluation of the BVE System for clinical performance including time needed to perform BVE, inter-operator variability and number of BVE non-diagnostic tests. |
| Device Under Investigation | Bluedop Vascular Expert (BVE) Model: Medical BVE100 Set 1: Tablet s/n 1001+ Charger s/n 1001 + Egg s/n 1002 |
| Number of Subjects Required for Inclusion in Clinical Investigation | 188 limbs required (188 subjects max., but enrolled number of subjects may be lower if, for certain subjects, both limbs are included in the study). |
| Clinical Investigation Design | Prospective, multi -center, nonrandomized, open label, single arm study |
| Primary Endpoint | Evaluation of clinical equivalence of BVE compared to Arterial duplex in the determination of presence or absence of significant PAD |
| Major Secondary Endpoints | Evaluation of clinical equivalence of BVE compared to ABPI in the determination of presence or absence of significant PAD. Evaluation of BVE safety |
| Subject Follow-up | N/A – No follow-up visits are planned in the study. |
| Inclusion Criteria | Subject must provide written informed consent prior to any clinical investigation related procedure. At least 18 years of age. Referred for duplex ultrasound of the lower limb (s) with suspected or previous history of peripheral arterial disease Must have an ABPI performed as part of the assessment |

Confidential Page 1 of 2

Document ref: CIP summary from BVE-01- v2.0

Date: 14Feb2022

| | 5. Able to obtain a brachial cuff blood pressure reading6. Must have a valid ankle duplex ultrasound measurement at the Posterior Tibial Artery (PTA) and Dorsalis Pedis Artery (DPA) |
|--------------------|---|
| Exclusion Criteria | 1. Subject is currently participating in another clinical investigation or has participated in another clinical investigation in the past 30 days prior to the start of the present study; |
| | 2. Pregnant or nursing subjects and those who plan pregnancy during the clinical investigation follow-up period |
| | 3. Presence of other anatomic or comorbid conditions, or other medical, social, or psychological conditions that, in the investigator's opinion, could limit the subject's ability to participate in the clinical investigation or to comply with follow-up requirements, or impact the scientific soundness. |
| | Inability of refusal to give informed consent. |
| | Lower extremity would or compromised skin of the legs that prevents access to the studied arteries. |

Confidential Page 2 of 2

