1.3 Clinical Investigation Design
The clinical investigation of the BVE for assessing PAD is a prospective, multi-center, open-label, non-randomized, single-arm study. The study has been designed to evaluate the clinical equivalence of BVE to arterial duplex in a group of patients referred for evaluation of PAD of the extremities when performed by a vascular specialist.
The study population is expected to be maximal 188 subjects (men and women over 18 years that were referred for arterial duplex ultrasound of the lower limb(s) with suspected or previous history of arterial disease and meet the study eligibility criteria).

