#### 2.1.2 Eligible population (EIP)

Eligible population (EIP) comprises the subset of enrolled patients who have at least one valid determination of PAD with both devices (BVE and arterial duplex).

•

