#### 2.3 Endpoint Analysis

#### 2.3.1 Primary endpoint

The primary endpoint of this study is the evaluation of the clinical equivalence of BVE compared to arterial duplex in the determination of presence or absence of significant PAD.

$$Overall\ accuracy = \frac{TN + TP}{TN + TP + FN + FP} = \frac{Number\ of\ correct\ assessments}{Number\ of\ total\ assessments}$$

Where TN = True Negative, TP = True Positive, FN = False Negative and FP = False Positive.

The primary endpoint is reached when it is shown that BVE is equivalent to the existing measurements (arterial duplex) in the determination of presence or absence of significant PAD (binomial outcome).

In order to determine the equivalence between BVE and arterial duplex measurements, a margin of
equivalence (D) is defined.
the event rates for the standard measurement group and the BVE measurement group can be defined as PS and PT, respectively. Therefore, equivalence will be confirmed if the difference between PS and PT is lower than the margin of equivalence D.
Ha: PS –PT < D

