2.3.2 Secondary endpoint(s)
The evaluation of clinical equivalence of BVE compared to ABPI in the determination of presence or absence of significant PAD will be carried out by means of the estimation of overall accuracy
$Overall\ accuracy\ calculation = \frac{TN + TP}{TN + TP + FN + FP} = \frac{Number\ of\ correct\ assessments}{Number\ of\ total\ assessments}$
Where TN = True Negative, TP = True Positive, FN = False Negative and FP = False Positive.
The secondary endpoint is met when it is shown that BVE is equivalent to the existing measurements (ABPI) in the determination of presence or absence of significant PAD (binomial outcome).
equivalence will be confirmed if the difference between $PS_2$ and $PT_2$ is lower than the margin of equivalence $D_2$ .
$Ha_2$ : $PS_2 - PT_2 < D_2$

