2.4 Sample Size Calculations

a maximum of 188 subjects will be enrolled in the clinical investigation in

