2.8 Study/ Trial Success
It will be considered a trial success when:

All subjects are successfully recruited

All required limbs are measured

 
All values are adequately collected and considered valid
 
At least the primary endpoint is met.
 

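### Second limbs of the same subject count fully toward the 188-limb target, and no visible text says how within-subject correlation enters the precision of overall accuracy

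*Protocol*

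**What the plan says.** The CIP summary in the protocol sets the target in limbs: "188 limbs required (188 subjects max., but enrolled number of subjects may be lower if, for certain subjects, both limbs are included". One subject with two limbs therefore replaces two subjects with one limb each.

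The SAP gives a number of subjects only as a ceiling. Section 1.3 has "The study population is expected to be maximal 188 subjects", and section 2.4 has "a maximum of 188 subjects will be enrolled in the clinical investigation in", where the visible sentence stops. No minimum number of subjects is visible beyond the 94 that 188 limbs imply by arithmetic.

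The eligible population in SAP 2.1.2 consists of enrolled patients "who have at least one valid determination of PAD with both devices", so subjects with one limb and subjects with two enter the same population. SAP 2.3.1 defines overall accuracy as correct assessments over total assessments. Section 2.3.2 uses the same formula for ABPI, where the evaluation "will be carried out by means of the estimation of overall accuracy". The visible decision rule in 2.3.1 is that "equivalence will be confirmed if the difference between PS and PT is lower than the margin of equivalence D". Section 2.8 makes trial success depend, among other things, on "All subjects are successfully recruited" and "All required limbs are measured".

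No visible text mentions within-subject correlation, a design effect, a clustered or robust variance, or a rule of one limb per subject.

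**The concern.** Two limbs of one person are measured by BVE in the same patient. SAP 2.9 itself plans comparisons by diabetes, smoking, hypertension and type of operator. These are features of the subject or the session rather than of the limb, so if they affect BVE performance, errors in the two limbs of a subject will tend to agree. The second limb then adds less information than a limb from a new subject.

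The relevant correlation is that of correct versus incorrect BVE results between the two limbs, not the correlation of disease. If it is positive and the analysis treats limbs as independent, the standard error of overall accuracy is too small and its interval too narrow. The primary endpoint is a pass/fail equivalence decision, so a misstated standard error matters most when the result lies close to the margin. The same holds for the ABPI comparison.

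**Working it through.** **The plan's own figure.** The 188 cannot be reproduced. The error rate, sidedness, power, expected rates and the value of D are not visible. A search over one-sided alpha 0.025 or 0.05, power 80% or 90%, rates of 0.50 to 0.99 and margins of 0.03 to 0.20, using several standard formulas, gave 266 combinations within tolerance of 188, of which 25 hit it exactly. The inputs cannot be inferred, and nothing here says that 188 is wrong.

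**Inputs.**
- 188 limbs, one or two per subject: CIP summary.
- f, the fraction of subjects with both limbs included: not given; assumed 0, 20%, 50% and 100%. The last is only an arithmetic bound, since the CIP summary speaks of certain subjects.
- rho, the within-subject correlation of correct/incorrect BVE results: not given; assumed 0.1 to 0.3.
- Accuracy: not given; assumed 90%.

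**Formulas.**
- Subjects = 188/(1 + f).
- Share of limbs from bilateral subjects = 2f/(1 + f).
- Design effect DE = 1 + rho × share.
- Effective limbs = 188/DE.
- Interval widening = √DE.
- 95% half-width = 1.96 × √(0.9 × 0.1 × DE/188).

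For example, f = 0.5 and rho = 0.3 give 188/1.5 = 125.3 subjects, share 1/1.5 = 0.667, DE = 1 + 0.3 × 0.667 = 1.200, 188/1.2 = 156.7 effective limbs and √1.2 = 1.095.

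| f | Subjects | rho | DE | Effective limbs | √DE | Half-width (points) |
|---|---|---|---|---|---|---|
| 0 | 188 | any | 1.000 | 188 | 1.000 | 4.29 |
| 0.2 | 156.7 | 0.1 | 1.033 | 181.9 | 1.017 | 4.36 |
| 0.2 | 156.7 | 0.3 | 1.100 | 170.9 | 1.049 | 4.50 |
| 0.5 | 125.3 | 0.3 | 1.200 | 156.7 | 1.095 | 4.70 |
| 1 (bound) | 94 | 0.3 | 1.300 | 144.6 | 1.140 | 4.89 |

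**Coverage.** Each scenario was simulated 40,000 times with 188 limbs, accuracy 0.9 and nominal 95% intervals. Entries are percentages.

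| Subjects (bilateral) | rho | Wald, limbs independent | Wilson, limbs independent | Wald, clustered by subject | Wilson on effective limbs |
|---|---|---|---|---|---|
| 188 (0) | – | 93.0 | 94.7 | 93.0 | 94.7 |
| 157 (31) | 0.1 | 92.7 | 94.6 | 93.4 | 95.4 |
| 157 (31) | 0.3 | 92.0 | 93.8 | 93.5 | 95.4 |
| 125 (63) | 0.3 | 90.5 | 92.5 | 93.6 | 94.9 |
| 94 (94) | 0.3 | 89.4 | 91.4 | 93.9 | 94.6 |

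The Wald interval covers only 93.0% when no subject is bilateral, so 93.0%, not 95%, is the fair comparator. Against it, clustering costs 0.3 to 1.0 points at 20% bilateral (93.0 − 92.7 and 93.0 − 92.0), 2.5 points at 50% and 3.6 points at the bound. The independent-limb Wilson interval shows the same pattern. The intervals that allow for clustering do not deteriorate. Repeat simulations agreed to within about half a point.

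**The case against.** The strongest reply is that the gap lies where text is withheld. Counting limbs is an openly stated design choice; it becomes a defect only if the sizing or the variance ignores clustering, and neither can be seen. SAP 2.4 breaks off in mid-sentence, 2.3.1 and 2.3.2 show gaps, and sections 2.2, 2.5 to 2.7 and 2.10 have no visible text. The abbreviation list includes confidence intervals and per-protocol terms that appear nowhere in the visible body, which suggests that more analysis text exists. This stands: the plan as a whole cannot be said to lack an adjustment.

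Nor do the supporting passages prove much singly. A formula for a point estimate would not carry a subject term, and a population definition does not fix a variance. They show only that the visible text leaves the matter open.

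The figures above also concern an interval for overall accuracy, whereas the visible decision rule compares PS − PT with D. For that difference the relevant correlation is that of signed disagreement (false negatives against false positives), which is not the rho used here. This stands too, and no direction is claimed for the PS − PT test or for power.

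Finally, the effect is small at a low bilateral share: at 20%, clustering costs less coverage than the Wald interval loses by itself. That is right, but the visible text sets no cap on the share, and the loss grows with it.

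**Conclusion.** The concern holds as limited to the visible text. The limb target does not depend on how many subjects are bilateral, and no visible rule tells the analyst to allow for it. An independent-limb analysis would misstate the precision of overall accuracy whenever BVE errors in a subject's two limbs are correlated.

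The size depends on a bilateral share, a correlation and an accuracy that are all assumed. There is no loss if no subject is bilateral or the correlation is zero. The effect is minor at 20% bilateral and no longer negligible at 50% with a correlation of 0.3. This is a point that should be fixed, held with medium confidence because the sizing and variance method cannot be seen.

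**What to change.** In SAP 2.3, state that the limb is the unit of analysis and the subject is the cluster. Compute confidence intervals and tests for overall accuracy, and for the paired PS − PT difference against duplex and against ABPI, with a subject-clustered variance: GEE with robust variance, or a bootstrap that resamples subjects. Report the number of bilateral subjects. In SAP 2.4, if the sizing assumed independent limbs, restate the precision or power of 188 limbs for the expected bilateral share. If withheld text already does this, the sponsor need only confirm it.

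The analysis change costs SAP wording and a few lines of code, with no new data and no extra patients. The price is somewhat wider intervals, of the size shown by √DE above, and a slightly less favourable stated precision. If that precision proves too low for the expected bilateral share, the sponsor would have to accept it, limit bilateral inclusion or add limbs. Fixing the method in advance also rules out choosing the variance after the results are known.

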#### 1.0 SYNOPSIS OF STUDY DESIGN

1.1	Purpose	of Statistical	Analysis	Plan
-----	---------	----------------	-----------------	------

This Statistical Analysis Plan (SAP) is intended to provide a detailed and comprehensive description of the planned methodology and analysis to be used for Clinical Investigation Plan (CIP) BVE-01-
1.2 Clinical Investigation Objectives
The primary objective of this study is to evaluate the clinical equivalence (accuracy assessment) of the BlueDop Vascular Expert (BVE) in comparison with arterial duplex ultrasound in the diagnosis of significant peripheral arterial disease (PAD) in a group of patients referred for evaluation of PAD of the lower limbs when performed by a vascular specialist.
1.3 Clinical Investigation Design
The clinical investigation of the BVE for assessing PAD is a prospective, multi-center, open-label, non-randomized, single-arm study. The study has been designed to evaluate the clinical equivalence of BVE to arterial duplex in a group of patients referred for evaluation of PAD of the extremities when performed by a vascular specialist.
The study population is expected to be maximal 188 subjects (men and women over 18 years that were referred for arterial duplex ultrasound of the lower limb(s) with suspected or previous history of arterial disease and meet the study eligibility criteria).

#### 1.4 Endpoints

#### 1.4.1 Primary performance endpoint

The primary performance endpoint is the evaluation of clinical equivalence of BVE compared to arterial duplex in the determination of presence or absence of significant PAD.

Equivalence will be evaluated through a binary result (either presence or absence of significant PAD) in BVE compared to a binary summary of the arterial duplex.

#### 1.4.2 Primary safety endpoint

To characterize and confirm the safety of BVE, safety will be evaluated by assessing the AEs and SAEs.

#### 1.4.3 Secondary endpoint

The secondary performance endpoint is to evaluate the clinical equivalence of BVE compared to the ABPI in a group of patients referred for evaluation of PAD of the lower limbs when performed by a vascular specialist.

Equivalence will be evaluated through a binary result (either presence or absence of significant PAD) in BVE compared to a binary summary of ABPI.

#### 2.0 ANALYSIS CONSIDERATIONS

2 4	۸na	lveic	Donu	lations
2.1	Ana	IVSIS	Popu	lations

ziiii ziiioiiiioiii populatioii (ziii /	2.1.1	Enrollment	population (	(EnP)
---	-------	------------	--------------	-------

Enrollment population (EnP) includes those subjects with at least one lower limb referred for evaluat	ion
of PAD.	

#### 2.1.2 Eligible population (EIP)

Eligible population (EIP) comprises the subset of enrolled patients who have at least one valid determination of PAD with both devices (BVE and arterial duplex).

•

#### 2.3 Endpoint Analysis

#### 2.3.1 Primary endpoint

The primary endpoint of this study is the evaluation of the clinical equivalence of BVE compared to arterial duplex in the determination of presence or absence of significant PAD.

$$Overall\ accuracy = \frac{TN + TP}{TN + TP + FN + FP} = \frac{Number\ of\ correct\ assessments}{Number\ of\ total\ assessments}$$

Where TN = True Negative, TP = True Positive, FN = False Negative and FP = False Positive.

The primary endpoint is reached when it is shown that BVE is equivalent to the existing measurements (arterial duplex) in the determination of presence or absence of significant PAD (binomial outcome).

In order to determine the equivalence between BVE and arterial duplex measurements, a margin of
equivalence (D) is defined.
the event rates for the standard measurement group and the BVE measurement group can be defined as PS and PT, respectively. Therefore, equivalence will be confirmed if the difference between PS and PT is lower than the margin of equivalence D.
Ha: PS –PT < D

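### As written, overall accuracy leaves out any limb with no final BVE result, so it can overstate performance if such limbs occur

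*SAP*

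**What the plan says.** SAP 2.3.1 defines overall accuracy against arterial duplex as (TN + TP) / (TN + TP + FN + FP): "Where TN = True Negative, TP = True Positive, FN = False Negative and FP = False Positive". The denominator is also described in words as the total of assessments, but the formula sets that total equal to the same four cells. SAP 2.3.2 says the comparison with ABPI "will be carried out by means of the estimation of overall accuracy" and repeats the formula.

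The BVE result has two categories. SAP 1.4.1 describes the primary comparison as "a binary result (either presence or absence of significant PAD) in BVE compared to a binary summary of the arterial duplex", and SAP 1.4.3 describes the secondary one as "a binary result (either presence or absence of significant PAD) in BVE compared to a binary summary of ABPI". Neither has a category for an inconclusive or missing BVE result.

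SAP 2.1.2 defines the eligible population as the "subset of enrolled patients who have at least one valid determination of PAD with both devices (BVE and arterial duplex".

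The protocol's inclusion criteria cover the two reference tests: "Must have a valid ankle duplex ultrasound measurement at the Posterior Tibial Artery (PTA) and Dorsalis Pedis Artery (DPA" and "Must have an ABPI performed as part of the assessment". No visible criterion requires a BVE result. The exploratory objectives include "time needed to perform BVE, inter-operator variability and number of BVE non-diagnostic tests".

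**The concern.** The primary objective is about patients referred for evaluation of PAD. When BVE gives no answer on a limb, it has not determined presence or absence of disease there. A measure that drops such limbs describes a narrower group, namely the limbs on which the device worked.

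The loss would fall mainly on the device under test. A valid duplex measurement is secured at entry, so for the primary endpoint BVE is the test that can still fail after enrolment. The protocol recognises that non-diagnostic tests may occur. If the affected limbs are also harder to classify, or if a missing answer is regarded as a failure, the reported accuracy is too favourable.

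The planned exploratory count does not close the gap. As worded it counts tests, and a test that is repeated successfully loses no limb. The number of tests therefore does not give the number of limbs lost, which is what a reader needs to bound the accuracy.

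**Working it through.** **The plan's own figure.** The only relevant number in the documents is the 188 limbs required (protocol, CIP Summary). It cannot be re-derived, because the significance level, power, expected rates and margin are not visible. The point does not depend on it; 188 serves below only as a convenient number of attempted limbs.

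**Where a limb without a BVE result goes.**

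1. TP and FP need a BVE result of PAD present; TN and FN need a result of PAD absent.
2. A limb with neither result fits no cell, so it is in neither the numerator nor the denominator.
3. The eligible population does not bring it back. A subject with no valid BVE result is outside that population. Because the definition is by subject, a subject with one answered limb stays in while the unanswered limb still falls out of the formula. The definition is supporting evidence only.

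**Formulas.** Let *a* be accuracy among answered limbs, *q* the share of attempted limbs with no final BVE result, and *b* the share of those limbs that would have been classified correctly.

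- Reported figure: *a*
- All attempted limbs: *a*(1 − *q*) + *bq*
- Overstatement: *q*(*a* − *b*)
- Worst case (*b* = 0): *a*(1 − *q*), lower than reported by *aq*
- Best case (*b* = 1): *a*(1 − *q*) + *q*, higher than reported by (1 − *a*)*q*

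The documents give none of *a*, *q* or *b*, so all values below are assumptions.

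**Bounds.**

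| *a* | *q* | Worst case | Best case |
|---|---|---|---|
| 90% | 0% | 90.0% | 90.0% |
| 90% | 2% | 88.2% | 90.2% |
| 90% | 5% | 85.5% | 90.5% |
| 90% | 10% | 81.0% | 91.0% |
| 80% | 5% | 76.0% | 81.0% |
| 80% | 10% | 72.0% | 82.0% |
| 95% | 5% | 90.25% | 95.25% |
| 95% | 10% | 85.5% | 95.5% |

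**Effect of repeat tests.** If a share *t* of limbs has a non-diagnostic first test and repeats resolve a share *r* of these, then *q* = *t*(1 − *r*). This assumes that limbs resolved by repeat have the same accuracy *a*. With *t* = 10%, *r* = 0, 50%, 80% and 100% gives *q* = 10%, 5%, 2% and 0%, which are the 90% rows above.

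**Whole limbs, 188 attempted, about 90% accuracy among those answered.**

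| No result | Reported | Worst case | Best case |
|---|---|---|---|
| 4 | 166/184 = 90.2% | 166/188 = 88.3% | 170/188 = 90.4% |
| 9 | 161/179 = 89.9% | 161/188 = 85.6% | 170/188 = 90.4% |
| 19 | 152/169 = 89.9% | 152/188 = 80.9% | 171/188 = 91.0% |

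If half of the unanswered limbs would have been right, the all-limb figure is (161 + 4.5)/188 = 88.0% with 9 lost and (152 + 9.5)/188 = 85.9% with 19 lost.

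**The case against.** The strongest objection is redaction. SAP numbering jumps from 2.4 to 2.8, 2.11 is an empty heading, 3.6 is listed in the contents with no visible body, and 2.3.1 and 2.3.2 themselves show gaps. A handling rule could sit in any of these places. This stands as a limit: the full plan cannot be said to lack such a rule, and the visible text does not rule out scoring an inconclusive test as FN or FP. It does not remove the point, which concerns a formula and a population that are visible, and the fix is conditional on the redacted text.

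Second, the formula is the ordinary definition of accuracy, and a reader might set its denominator against 188 to find the limbs lost. But 188 is a required number, and no visible text fixes or reports how many limbs were attempted. The shortfall would not reliably identify BVE failures.

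Third, no effect on a decision is shown. That is correct: no effect on PS − PT or on the margin D is claimed. SAP 2.8 makes complete measurement and valid values conditions of trial success. Read literally, unresolved limbs could block a success claim. That is a success condition, and it does not say how such a limb enters the accuracy figure.

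Fourth, size and direction are not established. This also stands. The true rate may be zero, repeats may resolve most failures, and the exclusion for skin that prevents access to the arteries may lower the rate. The bounds also run both ways, although at these accuracies the downside is much larger than the upside. Finally, the test-count wording comes from a two-page summary, so limb-level counts may be planned elsewhere.

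**Conclusion.** The concern holds on the visible text. Overall accuracy, against duplex and against ABPI, is conditional on BVE having given a result, and no visible rule says what happens to a limb on which it did not. Overstatement is possible but not certain. It arises only if some limbs end with no result, and only if those limbs count as failures or would have been classified less accurately than the rest.

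Under the worst-case convention the overstatement equals accuracy times the no-result rate: at 90% accuracy, 4.5 points if 5% of limbs have no result and 9.0 points if 10% do. These rates are assumed. With no such limbs the effect is zero. The change is worth making but is not critical; confidence is medium because of the redactions.

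**What to change.** Unless redacted text already does so, add the following to SAP 2.3.1 and 2.3.2 before results are known.

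- Pre-specify a sensitivity analysis of all limbs that have a valid reference result (duplex for the primary endpoint, ABPI for the secondary) and on which BVE was attempted. Count a limb with no final BVE result, after any permitted repeat, as not correct. Give a best-case bound that counts it as correct.
- Report the number and rate of such limbs by reference result (PAD present or absent).
- Keep the current figure, labelled as accuracy among diagnostic tests.

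The cost is SAP wording and one further table per endpoint. Non-diagnostic tests are already to be counted; the count must also be kept by limb. The downside for the sponsor is a companion figure that is less favourable by accuracy times the no-result rate.

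### The visible primary success rule in SAP 2.3.1 compares two event rates and, read literally, does not test overall accuracy; state the criterion directly on accuracy against duplex

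*SAP*

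**What the plan says.** The objective is framed as accuracy in both documents. The protocol's CIP summary (Objectives) says "Evaluate the clinical equivalence (assessment of accuracy) of BVE as binary result", and SAP 1.2 says "evaluate the clinical equivalence (accuracy assessment) of the BlueDop Vascular Expert (BVE) in comparison with arterial duplex ultrasound". SAP 1.4.1 sets a binary result "in BVE compared to a binary summary of the arterial duplex", so duplex is the reference.

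SAP 2.3.1 prints (TN + TP)/(TN + TP + FN + FP) and then moves to a different quantity: "the event rates for the standard measurement group and the BVE measurement group can be defined as PS and PT". The decision rule is "equivalence will be confirmed if the difference between PS and PT is lower than the margin of equivalence D", with the alternative written as PS – PT < D. The same section labels the PAD determination itself, present or absent, as the binomial outcome.

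SAP 2.3.2 says the ABPI comparison "will be carried out by means of the estimation of overall accuracy", yet its alternative has the same form, PS2 – PT2 < D2.

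SAP 2.8 lists among the conditions of trial success: "At least the primary endpoint is met". The rule in 2.3.1 therefore bears directly on the trial's verdict.

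**The concern.** No visible sentence makes PS or PT an accuracy, and no visible threshold is applied to the accuracy formula. Taken at its word, the rule asks whether duplex and BVE call PAD equally often, not whether they agree limb by limb. Two tests can have identical positive rates and still disagree on many limbs.

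The rule as printed also has one bound, although it is called equivalence. BVE calling more limbs positive than duplex moves PS – PT downwards, towards success.

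If that is the operative rule, BVE could be declared equivalent to duplex while misclassifying a substantial share of limbs. The same 2x2 table could pass on positive rates and fail on accuracy.

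**Working it through.** **Inputs.** From the documents: 188 limbs (CIP summary); one sample of patients with both tests, so the data are paired (SAP 2.1.2); rule PS – PT < D (SAP 2.3.1). Not visible, so assumed: D = 0.05, 0.10, 0.15, 0.20; one-sided 95% limits; prevalence of duplex-positive limbs 30–90%; independent limbs, although the CIP summary allows both limbs of a subject.

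**Does 188 reveal the rule?** No. Alpha, power and expected rates are not visible, so the figure cannot be reproduced from the plan's own inputs. Under assumed inputs, both kinds of calculation reach it:
- Two-rate non-inferiority (both rates 0.75, D 0.12, one-sided alpha 0.05, power 85%): (1.645 + 1.036)² × 2 × 0.75 × 0.25 / 0.12² = 187.2, rounded up to 188 per group.
- One-sample accuracy (0.75 against 0.65, one-sided alpha 0.025, power 80%): (1.960 × 0.477 + 0.842 × 0.433)² / 0.10² = 168.9, rounded up to 169; with 10% loss, 169/0.9 = 187.8, rounded up to 188.

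**What the rule measures under each definition.**
- Event = PAD-positive call: PS = (TP + FN)/N and PT = (TP + FP)/N, so PS – PT = (FN – FP)/N. Accuracy is 1 – (FN + FP)/N. One depends on the difference of the errors, the other on their sum.
- Event = correct assessment against duplex: PS = 1 by construction, and the rule becomes accuracy > 1 – D.
- PS = a benchmark accuracy: the rule becomes accuracy > PS – D.

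**One table.** TP = TN = 66, FN = FP = 28, N = 188. PS = PT = 94/188 = 0.50, so the difference is 0. SE = sqrt(56/188)/sqrt(188) = 0.0398. The 95% upper limit is 1.645 × 0.0398 = 0.065 (0.078 with 1.96), which passes D = 0.10. By symmetry the lower limit is –0.065, so a two-sided rule passes too. Accuracy is 132/188 = 70.2%.

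**Pass rates, sensitivity = specificity = 80%** (accuracy 80% at any prevalence; 400,000 simulated trials; SE = sqrt((fn + fp – (fn – fp)²)/N), with fn = FN/N and fp = FP/N):

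| Rule | Prevalence | D 0.05 | D 0.10 | D 0.15 | D 0.20 |
|---|---|---|---|---|---|
| Positive rates, one-sided | 30% | 99% | 100% | 100% | 100% |
| Positive rates, one-sided | 50% | 46% | 92% | 99.8% | 100% |
| Positive rates, one-sided | 70% | 0.6% | 16% | 71% | 98% |
| Positive rates, one-sided | 90% | 0% | 0% | 3% | 39% |
| Positive rates, two-sided | 30% | 0.1% | 16% | 71% | 98% |
| Positive rates, two-sided | 50% | 1.7% | 84% | 99.6% | 100% |
| Accuracy, exact lower limit > 1 – D | any | 0% | 0% | 0.02% | 4.5% |

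**Bar set by an accuracy criterion.** Exact one-sided 95% lower limit, 188 limbs:

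| Threshold | Minimum correct | Pass if true accuracy 90% | 95% | 97% |
|---|---|---|---|---|
| 0.95 | 184 | 0% | 4% | 33% |
| 0.90 | 177 | 3% | 77% | 99% |
| 0.85 | 169 | 58% | 99.9% | 100% |
| 0.80 | 160 | 99% | 100% | 100% |

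With a one-sided 97.5% limit the minima are 185/178/170/162.

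**Limit of accuracy on its own.** A device that calls every limb positive has accuracy equal to prevalence. At 90% prevalence it passes thresholds 0.95/0.90/0.85/0.80 in 0/3/58/99% of trials, so accuracy needs sensitivity and specificity beside it.

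**The case against.** The strongest reply is that the gap lies where the public copy is cut. In 2.3.1 the PS/PT sentence starts in mid-sentence, the value of D is not visible, and almost all of 2.4 is missing. An event definition, a confidence-limit rule or a link to accuracy could stand there. A reader might infer that the SAP never defines the event; the documents do not support that. The objectives and the wording of 2.3.2 also lean towards accuracy. If the hidden text follows them, the rule is already an accuracy threshold and only the drafting is awkward. This stands, and it limits the point. Against it, giving duplex an event rate of its own and calling the PAD determination the binomial outcome both fit the positive-call reading better, so that reading is not excluded.

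A reader might also infer that a device calling every limb positive would always succeed. That follows only from the one-sided form. Absolute-value bars may have dropped out of the available text, and with a two-sided bound such a device no longer passes at 30–70% prevalence. The cancellation of errors survives a two-sided bound.

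Nor is 1 – D the only possible threshold: if PS is a benchmark accuracy, it is PS – D.

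Finally, a reader might extend the fault to Ha2. SAP 1.4.3 leans towards ABPI as the reference, but 2.3.2 does not visibly say so. The protocol requires a valid duplex measurement in every subject. If duplex is the reference there, BVE and ABPI each have a genuine accuracy, and PS2 – PT2 < D2 is a sensible paired comparison.

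**Conclusion.** The point holds in a conditional form. The visible rule in 2.3.1 is written on two event rates and, on its literal reading, tests (FN – FP)/N rather than accuracy. For an 80%/80% device at 50% prevalence and an assumed D of 0.10, it passes 92% of trials one-sided and 84% two-sided, against 0% for a test that accuracy exceeds 0.90.

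The size depends on assumptions the documents do not show: D, the confidence level, prevalence and independent limbs. At small D or high prevalence the positive-rate rule often fails the same device, so the figures illustrate the fault and do not predict this trial's result.

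The public text does not support saying that the primary test is invalid. The rule should be rewritten before data are seen. That becomes essential if the unredacted SAP defines the event as a PAD-positive call, and is a change of wording only if it defines a correct assessment or a benchmark accuracy.

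**What to change.** In SAP 2.3.1, state that the primary endpoint is met if the lower confidence limit of overall accuracy against duplex, at a stated level, exceeds a pre-specified threshold. Derive the threshold from D on the accuracy scale: 1 – D if PS = 1, or PS – D if PS is a benchmark accuracy, with its value given.

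Report sensitivity and specificity with confidence intervals from the same 2x2 table next to the verdict. SAP 3.6, listed in the contents but not visible, may already cover this. Keep any PS – PT comparison of positive rates as supportive only, paired and two-sided (–D < PS – PT < D).

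Make the same change to Ha2 in 2.3.2 only if ABPI is the reference for TP and TN there, and name that reference either way.

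The cost is SAP text and no new data. If D was set on positive rates, the accuracy bar may be stricter, and the power for 188 limbs would need restating before data are seen, with allowance for subjects who contribute both limbs.
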